## 7 STUDY MATERIALS AND METHODS

### 7.1 DEVICE DESCRIPTION

RxSight's Light Adjustable Lens (LAL) is a silicone intraocular lens whose shape and focusing characteristics can be modified after implantation using an office-based UV light source, the RxSight Light Delivery Device (LDD), to improve uncorrected visual acuity and depth of focus.

#### 7.1.1 RxSIGHT LIGHT ADJUSTABLE LENS

The RxSight Light Adjustable Lens (LAL) is a foldable posterior chamber, UV filtering, three-piece photoreactive silicone lens with blue PMMA (polymethylmethacrylate) modified-C haptics, a 6.0 mm biconvex optic with squared posterior edge, and an overall diameter of 13.0 mm. The LAL optic design (Figure 1) also features a UV filtering posterior surface layer, to further enhance the UV absorbing properties of the LAL lens and limit retinal exposure.

**FIGURE 1: RxSIGHT LIGHT ADJUSTABLE LENS (LAL)**  
**(A) TOP VIEW AND (B) CROSS-SECTION VIEW OF THE OPTIC SHOWING  
LAL WITH A POSTERIOR LAYER**

A summary of the LAL design characteristics is presented below:

#### Lens Optic

- Material: Photo-reactive, UV absorbing Silicone
- Light transmission: UV cut-off at 10% T  $\geq$  392 nm for all lens power
- Index of refraction: 1.43
- Diopter power: +10 to +15.0 diopters and +25.0 to +30.0 D in 1.0 diopter increments; +16.0 to +24.0 diopters in 0.5 diopter increments
- Optic type: Biconvex
- Optic edge: Square on posterior surface and round on anterior surface
- Overall diameter: 13.0 mm
- Optic diameter: 6.0 mm

#### Haptics

- Configuration: Modified C
- Material: Blue polymethylmethacrylate
- Haptic angle: 10°

The LAL silicone material is designed to respond to a narrowband UV light by incorporating photoreactive components in the cross-linked silicone lens matrix. Post implantation, the LAL shape may be altered non-invasively (refractive power may be increased or decreased) by photoinitiation of a select spatial intensity profile. The silicone material contains photoreactive additive, which is selectively photo-polymerized in targeted areas upon exposure to the near UV light to alter the lens shape thus modifying spherical and spherocylindrical power of the LAL. The change in the shape becomes permanent when the remaining photoreactive additive is consumed following application of a non-profiled beam of the same ultraviolet light.

#### 7.1.2 LIGHT DELIVERY DEVICE (LDD)

RxSight's Light Delivery Device (LDD) is a UV light projection system (Figure 2) used to induce a predictable change in LAL power after implantation. RxSight's LDD consists of an anterior segment biomicroscope with the addition of an optical projection system, electronic control circuitry, and a UV source. The LDD delivers light profiles with adequate intensity and duration to induce polymerization of photoreactive additive leading to a refractive power change of the LAL. Because this procedure is performed after implantation, residual refractive errors can be minimized, reducing the need for spectacles, corneal refractive procedures, or additional IOL procedures to optimize a patient's vision.

**FIGURE 2: RXSIGHT LIGHT DELIVERY DEVICE (LDD)**

### 7.1.3 DEVICE MANUFACTURER

The LAL and LDD are manufactured by RxSight, Inc. located in Aliso Viejo, California (FDA Establishment Registration No. 3012712027). RxSight, Inc. has an established Quality Management System that is in conformance with the following standards:

- 21 C.F.R. Part 820 (Quality System Regulation)
- EN ISO 13485:2016 (Quality Management System with scope: design, manufacture, distribution and service of therapeutic, surgical and diagnostic devices and instruments especially for ophthalmology), and the Medical Device Directive 93/42/EEC.

The Sponsor will keep records to document the physical location of all investigational devices from shipment to the investigational sites until use, return or disposal. Traceability for both the LAL and LDD will be achieved by use of device serial numbers.

The principal investigator or an authorized designee shall keep records documenting the receipt, use, return, and disposal of the investigational devices, which shall include:

- The date of receipt
- Identification of each investigational device (batch number/serial number or unique code)
- The expiry date, if applicable
- The date or dates of use
- Subject identification

- Date on which the investigational device was returned/explanted from subject, if applicable, and
- The date of return of unused, expired or malfunctioning investigational devices, if applicable.

#### 7.1.4 INSERTION DEVICES

- The RxSight Insertion Device (K192926), which is comprised of a re-usable titanium injector and a single-use, non-preloaded polypropylene cartridge with lubricating coating, will be used as the primary device to insert the LAL and SofPort LI61AO IOL (Bausch + Lomb) into the eye.
- The Nichamin III Foldable Lens Inserter (Rhein Medical 05-2349) with the Nichamin II Foldable Lens Insertion Forceps (Rhein Medical 05-2348) can be used as back-up for the LAL only, if needed.

#### 7.1.5 INDICATIONS FOR USE

The Light Adjustable Lens and Light Delivery Device system is indicated for the reduction of residual astigmatism to improve uncorrected visual acuity after removal of the cataractous natural lens by phacoemulsification and implantation of the intraocular lens in the capsular bag, in adult patients:

- With pre-existing corneal astigmatism of  $\geq 0.75$  diopters
- Without pre-existing macular disease.

The system also reduces the likelihood of clinically significant residual spherical refractive errors.

## 7.2 SUBJECT ENTRY

If a COVID-related public health emergency declaration is in place at the time of the study, the study site should take appropriate measures in a clinic setting to minimize spread of the virus in conformance to professional society guidelines and applicable guidance from the states and counties in which the sites are located.

Patients who require bilateral cataract extraction and intraocular lens implantation and who wish to improve their depth of focus will be pre-screened for eligibility as part of pre-entry activity. If it is determined that the patient may be eligible to participate, delegated and trained study staff will explain the study purpose, procedures, risks/benefits and subject responsibilities to the potential participant. Procedures that are performed as part of a routine cataract evaluation and which (1) would be done whether or not study entry was contemplated (2) are done in accordance with the protocol-specific clinical methods (3) are completed within the protocol Preop window and (4) are done by trained team members on the delegation log may be performed and the results subsequently used for determining study eligibility without first obtaining consent.

Written informed consent must be obtained prior to initiation of any clinical procedures that are performed solely for the purpose of determining eligibility for research. The subject will sign and date the informed consent form in the presence of the person conducting the consent process. The investigator and/or the person conducting the consent process will also sign and date the consent form. The patient is enrolled upon signing the informed consent and a study ID is assigned.

The preoperative examination will be performed no more than 60 days prior to surgery for either the Primary eye or the Fellow eye. Both eyes of all subjects must be screened for eligibility at the same preoperative visit. If the 60-day time period elapses, it is acceptable for patients to be re-screened by undergoing a complete preoperative examination. If at any time during the preoperative screening, either eye does not meet inclusion or exclusion criteria, screening for that subject should be discontinued and the subject will be exited from the study. All study subjects must have preoperative keratometric astigmatism of <0.75 D in both eyes. Subject's eyes must meet all other applicable inclusion criteria and none of the exclusion criteria.

The principal investigator or delegated MD Sub-Investigator will review the Inclusion/Exclusion checklist document provided for the study and, if the subject is eligible, sign and date the form. The documentation of eligibility must be completed prior to implantation. Subjects that meet all inclusion/exclusion criteria will be randomly assigned in a 1:1 ratio to either the LAL group or the Control group. In addition, each eye of the subject will be assigned as either the primary eye or the fellow eye based on randomization. Pre-determined randomization schemes will be utilized. A randomization schedule for the treatment assignments (LAL versus Control) with a block of 4 and a ratio of 1:1 will be generated using a random generator such as SAS. Randomization of subjects will occur immediately prior to commencing cataract surgery on the primary eye. Only subjects meeting all inclusion/exclusion criteria may be implanted. Those subjects who do not meet the inclusion/exclusion requirements will be considered screen failures. Exit forms will be completed for all screen fails. Up to 350 subjects may be enrolled to allow for up to 230 subjects who will have had implantation of the LAL IOL or Control IOL attempted in the FAS. An additional 17 subjects were implanted in the pre-COVID-19 population.

The implant lens powers for the LAL and Control IOLs will be calculated based upon ocular biometry data and a lens power formula of the investigator's choice. Optimized lens constants of the investigator's choice also may be utilized. These lens constants will not be changed during the clinical investigation. For all study eyes, a postoperative spherical equivalent (SE) outcome closest to emmetropia as measured on a 4 meter exam lane will be targeted. The lens power will not be altered based on intraoperative diagnostics.

Subjects randomized to the LAL group

Commencing at the Postop Week 3 [REDACTED] visit (17-24 days post-Fellow eye operative visit), both eyes will receive an [REDACTED]  
[REDACTED]

At the Adjustment #1 visit (3-7 days after the Postop Week 3 [REDACTED] visit), both eyes will receive an adjustment #1 light treatment based on the measured manifest refraction at 4 meters at this visit. Eyes measured with a manifest cylinder of  $\geq 0.50$  D will receive a spherocylindrical light treatment while eyes with  $< 0.50$  D of manifest cylinder will receive a non-astigmatic light treatment.

At the Adjustment #2 visit (3 to 7 days after the Adjustment #1 visit), both eyes will receive an adjustment #2 light treatment also based on the measured manifest refraction at 4 meters at this visit. Eyes measured with a manifest cylinder of  $\geq 0.50$  D will receive a spherocylindrical light treatment while eyes with  $< 0.50$  D of manifest cylinder will receive a non-astigmatic light treatment.

Three to 7 days after the Adjustment #2 light treatment, both eyes will be eligible to receive an adjustment #3 light treatment. If the eye's |MRSE| is  $\geq 0.25$  D OR manifest cylinder is measured at  $\geq 0.50$  D, then the eye will receive an adjustment #3 light treatment; otherwise the eye will be eligible to proceed to lock-in #1.

The lock-in #1 light treatment will be performed in the primary eye 3 to 7 days after the subject's final adjustment light treatment followed 3 to 7 days later by the lock-in #2 treatment, if needed. The lock-in #1 treatment will be performed in the fellow eye 3 to 7 days after the final lock-in in the primary eye and after confirmation that there has been no ultraviolet (UV) retinal damage per Sections 7.3.2.1 and 7.3.2.2 followed 3 to 7 days later by lock-in #2, if needed. Subjects in the LAL group will receive [REDACTED], up to three spherocylindrical/non-astigmatic light treatments, and one or two lock-in treatments in each eye.

Examinations will occur at regular intervals over a 6 month period to evaluate the safety and effectiveness outcomes. For eyes in the LAL group, if an eye is diagnosed with ultraviolet (UV) retinal damage, an additional follow-up exam will be added at 12 months postoperatively to confirm resolution or document sequelae, if any. Masked examiners will be utilized at the Postop Month 6 visit.

Safety for all study eyes will be evaluated per ISO 11979-7.

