### 4 STUDY DESIGN

A prospective, randomized, controlled, multi-center, clinical study will be conducted at a maximum of 11 sites located in the United States. Subjects will be followed for a 6 month period. A minimum of 20 subjects will undergo study implantation at each participating site, with less than 25% of the total study population implanted at one clinical site.

Patients who require bilateral cataract extraction and intraocular lens implantation and who wish to improve their depth of focus will be pre-screened for eligibility as part of pre-entry activity. If it is determined that the patient may be eligible to participate, delegated and trained study staff will explain the study purpose, procedures, risks/benefits and subject responsibilities to the potential participant. Written informed consent must be obtained prior to initiation of any clinical procedures that are performed solely for the purpose of determining eligibility for. The patient is enrolled upon signing the informed consent. Both eyes of all subjects must be screened for eligibility at the same preoperative visit. If at any time during the preoperative screening, either eye does not meet inclusion or exclusion criteria, screening for that subject should be discontinued and the subject will be exited from the study. Subjects that meet all inclusion/exclusion criteria will be randomly assigned in a 1:1 ratio to either the LAL group or Control group. In addition, each eye of the subject will be assigned as either the primary eye or fellow eye. Pre-determined randomization schemes will be utilized. The primary eye of each subject will be scheduled for surgery first with implantation of the fellow eye separated by 7 to 14 days.

All study eyes will be targeted for post cataract surgery emmetropia as measured on a 4 meter exam lane. If surgical complications (either prior to attempting to implant the study IOL or after study IOL implantation has been attempted) occur with the primary eye and no IOL is implanted,

the subject should be followed until any adverse event that may have occurred is stable or has resolved per the investigator's assessment; at which time the subject should be exited from the study. No study IOL should be implanted in the fellow eye. Subjects that have successful implantation of a study IOL in the primary eye but not the fellow eye will not be required to have monocular clinical measurements of their fellow eye performed throughout the study.

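### Section 7.2 discloses a fixed block of 4 to unmasked surgeons; if blocks run within site, which the plan does not say, a third of assignments are certain in advance

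*Combined protocol and SAP*

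**What the plan says.** Section 7.2 (Subject Entry) of the combined protocol and SAP describes the scheme in three statements: "Subjects that meet all inclusion/exclusion criteria will be randomly assigned in a 1:1 ratio to either the LAL group or the Control group"; "Pre-determined randomization schemes will be utilized"; and "A randomization schedule for the treatment assignments (LAL versus Control) with a block of 4 and a ratio of 1:1 will be generated". On timing it says: "Randomization of subjects will occur immediately prior to commencing cataract surgery on the primary eye". On eligibility paperwork: "The documentation of eligibility must be completed prior to implantation".

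Section 4 says the study "will be conducted at a maximum of 11 sites located in the United States" and adds: "A minimum of 20 subjects will undergo study implantation at each participating site". Section 7.2 also allows more consents than implantations: "Up to 350 subjects may be enrolled to allow for up to 230 subjects who will have had implantation" attempted.

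The readable text does not state whether the schedule is stratified by site, who holds it, or how an assignment reaches the operating room.

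Masking is described only for the Month 6 examiners (Section 4, Tables 1 and 2). Sections 7.3.1 and 7.4 name the lens for each arm. Only LAL subjects receive UV spectacles and light treatments (Sections 7.3.1 and 7.3.2). That site staff know each past assignment is therefore an inference, but a safe one.

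Some entry criteria rest on judgement. Section 6.1 accepts the surgeon's own estimate of potential acuity, and Section 6.2 excludes subjects whom the doctor thinks cannot hold fixation.

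**The concern.** A single known block size lets anyone who sees a block's earlier assignments work out the later ones. Here the people who see past assignments also decide who is eligible. A surgeon who expects LAL next could enter a subject with a better visual prognosis, or hold back a borderline one, without ever seeing the list.

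The co-primary endpoints in Section 8.5.1 would be exposed in different ways:

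- DCIVA and BCDVA are compared between arms. The primary test is not readable, but the tipping-point analysis in Section 8.5.2 uses a two-sample t-test, which does not adjust for prognosis.
- Depth of focus is compared numerically, with no test.
- The DCIVA responder rate is a proportion in the LAL arm alone, so steering better eyes to LAL would raise it directly.

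The deadline for eligibility paperwork adds a smaller gap. Only eligible subjects are to be randomised, yet the sign-off is due before implantation, not before randomisation. As written, the document could be completed after the assignment is known.

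**Working it through.** **Inputs.** Block 4 and ratio 1:1 (Section 7.2); up to 11 sites with at least 20 subjects each (Section 4); up to 230 subjects with implantation attempted (Section 7.2).

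**The plan's own figure.** The plan states no predictability figure. Its group size reproduces: 100 / 0.90 = 111.1, rounded up to 112 per group (Section 8.1.2), or 224 in total against the cap of 230. Spread over 11 sites, 230 / 11 is about 21 per site.

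**Case A: blocks run within site.** There are 6 equally likely orders of two LAL and two Control. The best guess is the arm that is behind so far.

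| Position in block | Certain in advance | Best guess right |
|---|---|---|
| 1 | 0 | 1/2 |
| 2 | 0 | 2/3 |
| 3 | 1/3 (first two alike) | 1/3 × 1 + 2/3 × 1/2 = 2/3 |
| 4 | 1 | 1 |

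- Certain: (0 + 0 + 1/3 + 1) / 4 = 8/24 = 33.3%.
- Best guess right: (1/2 + 2/3 + 2/3 + 1) / 4 = 17/24 = 70.8%.
- For a site with 20 subjects: 20 × 1/3 = 6.7 certain assignments, and 20 × 17/24 = 14.2 correct guesses against 10 by chance.

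**Case B: one list shared across sites.** In a simulation of 11 sites with 21 subjects each (4,000 runs), sites entered subjects in random order and each saw only its own assignments. Guesses were right 50.7% of the time. Runs of consecutive subjects from one site would raise this somewhat; that was not computed.

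**What steering could do (illustrative).** Assume every site enters a subject whose outcome is *s* SD better when it guesses LAL and *s* SD worse when it guesses Control, with no true difference.

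- In Case A the bias in the arm difference is 2 × (2 × 17/24 − 1) × *s* = 0.833 *s*. With 21 subjects per site only 20 fall in complete blocks, so it is 0.833 × 20/21 = 0.794 *s*.
- For *s* = 0.1 the bias is 0.079 SD. With 231 / 2 = 115.5 per arm, the standard error is √(2/115.5) = 0.132 SD. The test statistic shifts by 0.079 / 0.132 = 0.60, and the chance of exceeding 1.96 is about 8.7%.

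Simulated one-sided rejection rates (nominal 2.5%) agree:

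| Assumed *s* | Per-site blocks of 4 | Per-site random 4/6 | Shared list, blocks of 4 |
|---|---|---|---|
| 0.1 | 8.8% | 8.0% | 2.9% |
| 0.25 | 30.8% | 27.0% | 3.0% |
| 0.5 | 82.7% | 75.0% | 3.6% |

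The values of *s* are assumptions. The documents give nothing from which to estimate them.

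**Effect of varying block sizes (per-site lists, 20 assignments).** Assume a site knows which sizes are in use but not their sequence. Random 4/6 blocks then cut certain assignments from 33.3% to about 5.7%, and best-guess accuracy from 70.8% to about 68.5%. With 4/6/8 the figures are about 2.4% and 67%.

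**The case against.** The strongest reply is that Section 7.2 speaks of a schedule in the singular and mentions no site stratification. If the list is shared and a site sees only its own assignments, guessing is close to chance and the disclosed block size does almost no harm. This stands, and it makes the concern conditional. A reader might infer that surgeons in this trial can predict the next assignment; the documents do not support that, because they never say that blocks run within site or that a site sees other sites' assignments.

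A reader might also infer that the site controls the order of its surgery list. That is plausible, but no section says who orders it. The investigator's choice of lens power formula is not shown to be a selection route either. Section 7.2 sets one refractive target for all study eyes and freezes the lens constants, and DCIVA and BCDVA are measured with distance correction.

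Several safeguards are real but partial:

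- Late randomisation limits reaction to a revealed assignment, not anticipation of the next one.
- Sections 6.1 and 6.2 narrow the prognostic range, which limits how far steering could go.
- Baseline summaries by arm and by site (Section 8.4), and site as a covariate (Section 8.5.3), could show imbalance in measured factors only.
- Masked examiners protect the Month 6 measurement, not entry into the study.

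**Conclusion.** The concern holds in conditional form. A single block size of 4 is disclosed to investigators who know each lens implanted and who apply judgement-based entry criteria. If blocks run within site, 33.3% of assignments are certain and a best guess succeeds 70.8% of the time. If one list is shared across sites, with each seeing only its own assignments, the figure is about 51% and the risk is close to nil. The readable text does not settle which case applies, so concealment cannot be verified from it.

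The two percentages for per-site blocks are exact. The shared-list figure rests on 11 sites entering subjects in random order. The inflated error rates rest on steering at every site and show sensitivity only; they are not evidence that any selection took place.

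**What to change.** For subjects not yet randomised:

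1. State whether the list is per site or shared, who holds it, and how assignments are released. Keep a shared list shared: going from shared blocks of 4 to per-site 4/6 would raise best-guess accuracy from about 51% to about 68.5%.
2. Use randomly varying block sizes, for example 4 and 6. Remove the block size from the protocol and all site-facing documents, and hold it in a restricted randomisation file.
3. Release each assignment centrally, one subject at a time.
4. Require eligibility sign-off before randomisation rather than only before implantation.

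The cost is a new list and a short amendment, which may need IRB or other regulatory approval under Section 11.8. An unfinished block of 6 can leave an imbalance of at most 3 subjects per list, against 2 with blocks of 4.

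The benefit has limits. Under per-site lists, varying blocks remove most certain predictions but leave best-guess accuracy near 68.5%, so steps 3 and 4 are needed as well. Earlier disclosure of the block size cannot be undone.

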### 7.3 LAL IMPLANTATION AND REFRACTIVE ADJUSTMENT

Each investigative site will follow a standard regimen of pre-, intra-, and postoperative medications to be used in the study that has been reviewed and approved by the study medical monitor. This standard regimen will also specify the ophthalmic viscoelastic device to be used during surgery.

